## Statistical Analysis Plan

The analysis sets which will be used in analyses of the various endpoints are shown in Table 3.

**Table 3. Summary of Outcome Populations and Analysis Sets**

| Outcome variable                    | Populations                 |
|--|------------------------------------|
| Efficacy data                       |                                    |
| Disposition                                | All Patients, Full analysis |
| Demography                                 | Safety                      |
| OR*, disease control, DOR*, PFS, OS, OS-12 | Efficacy                    |
| Safety data                         |                                    |
| Relevant Medical History                   | Safety                      |
| Current Medical Condition at Entry         | Safety                      |
| Exposure                                   | Safety                      |
| Adverse events (including SAEs and DLTs)   | Safety                      |
| Laboratory measurements                    | Safety                      |
| Vital signs                                | Safety                      |
| Physical examinations                      | Safety                      |
| ECGs                                       | Safety                      |
| Pharmacokinetic data                | Pharmacokinetic             |
| Pharmacodynamic data                | Pharmacodynamic             |

\* Patients who are evaluable for the analysis of OR and DOR are those with measurable disease at baseline

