7.7.4 Definition of maximum tolerated dose

A dose will be considered non-tolerated and dose-escalation will cease if $\geq 33\%$ of patients on that dose experience a DLT. Once the non-tolerated dose is defined, the MTD will be confirmed at a dose level below the non-tolerated dose or a dose between the non-tolerated dose and the last tolerated dose may be investigated. At least 6 evaluable patients are required to determine the MTD.

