### **4.5. PRIMARY SAFETY ENDPOINTS**

#### **4.5.1. Dose-escalation and Safety cohorts Part A**

The primary safety endpoints for Part A include:

- Maximum-tolerated dose (MTD) based on patients who completed the DLT evaluation
- AEs, SAE, laboratory evaluations, vital signs, and physical examinations
- Treatment-emergent AEs (TEAEs), SAEs and deaths, graded in accordance with National Cancer Institute Common Terminology Criteria for Adverse Events (NCI CTCAE) v4.03.

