**Table 2. Definition of Analysis Populations**

| Analysis Set    | Definition  |
|------------------------|--|
| All Patients           | All patients who provided written informed consent (i.e., including screen failures)   |
| Full Analysis          | All patients who were either assigned or randomized to study.  |
| Safety                 | All patients who received at least 1 dose of AZD9150, AZD5069, or MEDI4736.  |
| Pharmacokinetics (PK)  | All dosed patients with reportable AZD9150, AZD5069, treme or MEDI4736 plasma concentrations except for important protocol deviation. The important protocol deviations will be determined by the clinical team during the Blind Data Review Meeting (BRDM) planned to take place just prior to the final Database Lock (DBL). |
| Pharmacodynamics (PDN) | All patients who provided biological samples for pharmacodynamic research except for important protocol deviation. The important protocol deviations will be determined by the clinical team during the Blind Data Review Meeting (BRDM) planned to take place just prior to the final Database Lock (DBL).                    |

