## Statistical Analysis Plan

### 6. GENERAL ASPECTS FOR STATISTICAL ANALYSIS

#### 6.1. GENERAL METHODS

Statistical analyses of the demographic, safety, and efficacy data will be performed by [REDACTED] under the direction of the Early Clinical Biometrics Group, AstraZeneca.

[REDACTED] will perform all PK and PD analyses. [REDACTED] will provide data listings of the administration information for the collection of PK and PD samples. [REDACTED] will provide summaries of descriptive statistics for the PK and PD parameters derived by [REDACTED].

AstraZeneca will be responsible for creating the playbook used to communicate CRM model recommendations to the SRC in dose-escalation Part A. However, [REDACTED] will independently generate a copy of the playbook that can serve as a back-up, if needed. AstraZeneca will also be responsible for providing all summaries of predictive probability calculations to be performed in Part B.

The methods outlined below apply to both Part A and Part B unless otherwise specified.

- SAS version 9.3 or higher will be for all statistical analyses, excluding analyses that are Bayesian or involve the CRM.
- R version 3.1.2 or higher software and modules (e.g.: dferm package) will be used for CRM analyses in Part A and for the Bayesian analyses in Part B.
- All patients who provided informed consent will be accounted for in this study and have data from patients who were randomized or dosed included in the patient data listings.
- Listings will be sorted by treatment group (see Section 6.1.1 for ordering), patient number and, if applicable, by assessment date and time unless otherwise noted. Patients who are screen failures will be presented in a separate listing.
- The total number of patients in the treatment group and dose level (N) will be used as the denominator for percentage calculations, unless stated otherwise in the table shell.
- Continuous variables, including pharmacodynamic variables, will be summarized using the number of observations (n), mean, standard deviation (StD), median,

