## Statistical Analysis Plan

A CRM-based approach will be used to identify the set of AZD9150/MEDI4736 and AZD5069/MEDI4736 dose combinations where the incidence of DLT is no larger than 33%. In each cohort, up to 3 patients will be initially assessed. Dose escalation to the next higher dose level for the next cohort group of 3 patients will occur if all 3 patients in the initial cohort complete Cycle 1 without DLT. Following the first DLT, the CRM model will be run and the output made available to the SRC to guide further dosing decisions (see Section 11.1.2 for details).

Tolerated combination doses will be defined as combinations for which the DLT incidence is no larger than 33%. Prior to the occurrence of the first DLT, a cohort will consist of 3 patients; following the first DLT, cohorts will require a minimum of 6 patients before dose escalation may occur. In all cohorts, the sample size refers to patients who are evaluable for dose escalation; patients who are nonevaluable for dose escalation will be replaced (See Section 5.4.3 of the study protocol for the criteria to be deemed evaluable for dose-escalation purposes).

Dose escalation will be defined as an increase in the dose of at least 1 of the drugs without decreasing the dose of the other.

Dose escalation for the 2 combination treatments (ie, AZD9150/MEDI4736 and AZD5069/MEDI4736) will advance independent of each other. In addition to determining DLT in the DLT evaluation period, the SRC will critically review all available data pertaining to safety, tolerability, and IM as well as PK, pharmacodynamic, and antitumour activity before deciding on the next dose levels to be explored. Dose escalation in each arm will be considered completed once 1 of the following criteria is met:

- The MTD (for definition of MTD see Section 5.3.3 of the study protocol) for the 2 agents in combination have been identified
- The SRC has recommended doses for the 2 agents in combination to be further explored in the dose-expansion Part B
- The maximum doses of the 2 agents in combination have been reached (ie, AZD9150 3 mg/kg IBW, AZD5069 120 mg BID [for a maximum total daily dose of 240 mg], and MEDI4736 20 mg/kg)

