### 11.1.3. Confirmation of the Presumed Recommended Dose

Once the MTDs for each of the 2 agents in combination with MEDI4736 have been identified or the maximum doses of each of the 2 agents in combination with MEDI4736 have been reached, the SRC may decide to enrol an additional cohort of at least 6 evaluable patients per treatment arm to confirm the presumed recommended dose for each of the 2 agents in combination with MEDI4736 to be further explored in the dose-expansion Part B.

Once all patients have completed Part A, the final estimates of the proportion of DLTs for each tested dose-level of the 2 combination will be summarized.

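### SAP Table 3 puts DLTs on the Safety set and Table 2 has no DLT-evaluable set, so the reported Part A DLT rates can be diluted by replaced patients; the dose decisions are not affected

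*SAP*

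**What the plan says.** Two parts of the SAP point to different populations.

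**Toward all treated patients**
- Table 3 maps the row "Adverse events (including SAEs and DLTs") to the Safety set. It footnotes evaluability for objective response and duration of response, but not for DLTs.
- Table 2 defines the Safety set as "All patients who received at least 1 dose of AZD9150, AZD5069, or MEDI4736". No DLT-evaluable set is listed.
- Section 6.1 sets the default: "The total number of patients in the treatment group and dose level (N) will be used as the denominator for percentage calculations". It allows a table shell to say otherwise. Section 15 places the mock-ups in separate documents.

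**Toward DLT-evaluable patients**
- Section 4.5.1 gives the Part A primary safety endpoint as the "Maximum-tolerated dose (MTD) based on patients who completed the DLT evaluation". The opening of Section 11 repeats this focus.
- Section 11.1.1 counts cohort size in evaluable patients, and "patients who are nonevaluable for dose escalation will be replaced".
- Section 11.1.2 builds the CRM playbook from evaluable patients only.
- Section 6.2 defines the evaluable patient for Arms A1, A4 and A2, by minimum dosing or by having had a DLT.

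The closing summary in Section 11.1.3 says that "the final estimates of the proportion of DLTs for each tested dose-level of the 2 combination will be summarized". It names no denominator.

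The limit itself is in SAP 11.1.1 ("Tolerated combination doses will be defined as combinations for which the DLT incidence is no larger than 33" per cent) and in Protocol 7.7.4, where a dose is non-tolerated if at least 33% "of patients on that dose experience a DLT". Protocol 7.7.4 also asks for at least 6 evaluable patients to determine the MTD.

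**The concern.** The dose is chosen on one denominator, and its DLT rate would by default be reported on another. A replaced patient leaves the cohort count but stays in the Safety set. If such patients bring no DLTs, each one lowers the tabulated percentage. The study report could then show a rate under 33% for a dose level whose evaluable patients sat at the limit. A reader could not tell that from the table, and SAP Section 13, on changes from the protocol, does not mention it.

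**Working it through.** **Inputs.** The limit is 33% and the minimum is 6 evaluable patients (Protocol 7.7.4; SAP 11.1.1). In Arm A3, 6 patients are dosed first and 2 or more with a DLT trigger a reduction (Protocol 7.7.1). The number of replaced patients, *m*, is not in the documents, so 1 to 4 per dose level is assumed.

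**1. The plan's own rule.** 2/6 = 33.3% reaches the limit and 1/6 = 16.7% does not. The A3 count rule and the 33% limit therefore agree.

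**2. Dilution.** With *d* DLTs in *n* evaluable patients, the evaluable rate is d/n. If the replaced patients have no DLT, the Safety-set rate is d/(n+m).

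| Evaluable result | Smallest *m* that brings it under 33% | Safety-set rate |
|---|---|---|
| 2/6 = 33.3% | 1 | 2/7 = 28.6% |
| 3/9 = 33.3% | 1 | 3/10 = 30.0% |
| 4/12 = 33.3% | 1 | 4/13 = 30.8% |
| 3/6 = 50.0% | 4 | 3/10 = 30.0% |

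For 2/6, further replacements give 2/8 = 25.0% and 2/9 = 22.2%. A result clearly above the limit takes several replacements to cross it.

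**3. How often the boundary arises.** With n = 6 and m = 1 to 3, only exactly 2 DLTs crosses. Its probability is 15p²(1−p)⁴:
- true rate 0.20: 24.6%
- 0.31: 32.7%
- 0.33: 32.9%
- 0.40: 31.1%
- 0.57: 16.7%

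The simulation averages in Protocol 8.2.1 imply rates at the true MTD of 1.5/4.8 = 31% (AZD9150) and 1.4/4.5 = 31% (AZD5069). A boundary result is therefore quite likely near the target dose.

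**4. Direction of the bias.** Under SAP 6.2 a patient with a DLT in the first 35 days is evaluable, so non-evaluable patients add nothing to the numerator and the bias is downward. Two gaps limit this:
- SAP 6.2 does not cover Arm A3.
- Protocol 7.7.5 gives Arms A2 and A3 no DLT alternative. It requires minimum dosing and being active at the end of Day 35.

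On the protocol wording, an A2 or A3 patient who stops early because of a DLT is non-evaluable but still has a DLT. As an illustration, take six protocol-evaluable patients with one DLT plus one such patient. The evaluable rate is 1/6 = 16.7% and the Safety-set rate is 2/7 = 28.6%, so the direction reverses.

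**5. Arm A6.** Protocol 4.1.2 says A6 is not followed for DLTs, but its patients are in the Safety set and receive the same regimen as the upper A1 cohort. SAP 6.1.1 groups Part A by treatment combination, while Protocol 8.10 presents data by cohort. Pooling A6 into a DLT denominator is thus possible but not stated.

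**The case against.** The strongest reply has five parts.

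- **The default can be overridden.** SAP 6.1 yields to the table shells, which are not available, and the DLT shell may name the evaluable denominator. This stands as a condition. The SAP text itself contains no override, and Table 3 states the Safety set outright.
- **Section 11.1.3 may already use evaluable patients.** It closes the part of the SAP on identifying the MTD, where cohort size and playbook are both on that basis. This stands: a reader might infer that the final proportions are definitely on the Safety set, but the text leaves it open. The DLT tables in Section 11.3 are more clearly governed by Table 3.
- **No dose decision changes.** A reader might infer that dilution could get a non-tolerated dose accepted. The documents do not support that. The SRC determines the MTD (SAP 3.6.1 and 11.1.2), and the playbook it receives uses evaluable patients only. Protocol 7.7 reports that the Arm A1 and A2 doses had been identified by Amendment 5.
- **No actual boundary case is shown.** In the one cohort with both a DLT count and a number of patients, Arm A3 (Protocol 4.1.2), there was one DLT among the first 6. That is 16.7%, under the limit on any denominator.
- **DLTs in all treated patients are a legitimate safety display.** They are, as a count or listing. As a percentage to be read against a limit defined for evaluable patients, they are not.

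**Conclusion.** The SAP is inconsistent with itself. Table 3, with the Section 6.1 default, puts DLTs on all treated patients, while Sections 4.5.1, 11, 11.1.1 and 11.1.2 rest on DLT-evaluable patients. Evaluability is defined in Section 6.2 but never becomes an analysis set.

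The consequence is confined to the reported DLT rate. At the boundary, one replaced patient lowers it from 33.3% to 28.6% (n = 6), 30.0% (n = 9) or 30.8% (n = 12). This rests on three assumptions: no table shell overrides the default, at least one patient at that dose level was replaced, and the SAP 6.2 definition applies, so that replaced patients carry no DLT. Escalation and the MTD are untouched.

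This is a should-fix point: it concerns the figures reported beside the Part A primary endpoint, but the effect is descriptive and its actual size is unknown.

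**What to change.** 1. **Reconcile the definitions first.** SAP 6.2 and Protocol 7.7.5 must agree for Arms A2 and A3, with A3 covered, so that the set cannot exclude a patient who had a DLT. Protocol 4.1.2 has a sentence treating patients with a DLT as evaluable, but it follows the A4 text and its scope is unclear. The A4 wording also needs a check: it asks for at least 3 AZD9150 doses in Cycle 1, while the every-2-week cohort has 28/14 = 2 planned.
2. **SAP Table 2:** add a DLT-evaluable set for the arms assessed for DLT (A1 to A4, not A6).
3. **SAP Table 3:** give DLTs their own row on that set, leaving other adverse events on the Safety set.
4. **SAP 11.3 and 11.1.3:** name that set as the denominator for DLT percentages and for the final proportions by dose level.
5. **Keep a listing** of DLTs in all treated patients.

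The cost is a row in each of two tables, a few words in two sections, and agreement on one definition. Evaluability already has to be classified for the playbook, so no new data are needed. The reported DLT rates may come out less favourable.

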## Statistical Analysis Plan

### 6. GENERAL ASPECTS FOR STATISTICAL ANALYSIS

#### 6.1. GENERAL METHODS

Statistical analyses of the demographic, safety, and efficacy data will be performed by [REDACTED] under the direction of the Early Clinical Biometrics Group, AstraZeneca.

[REDACTED] will perform all PK and PD analyses. [REDACTED] will provide data listings of the administration information for the collection of PK and PD samples. [REDACTED] will provide summaries of descriptive statistics for the PK and PD parameters derived by [REDACTED].

AstraZeneca will be responsible for creating the playbook used to communicate CRM model recommendations to the SRC in dose-escalation Part A. However, [REDACTED] will independently generate a copy of the playbook that can serve as a back-up, if needed. AstraZeneca will also be responsible for providing all summaries of predictive probability calculations to be performed in Part B.

The methods outlined below apply to both Part A and Part B unless otherwise specified.

- SAS version 9.3 or higher will be for all statistical analyses, excluding analyses that are Bayesian or involve the CRM.
- R version 3.1.2 or higher software and modules (e.g.: dferm package) will be used for CRM analyses in Part A and for the Bayesian analyses in Part B.
- All patients who provided informed consent will be accounted for in this study and have data from patients who were randomized or dosed included in the patient data listings.
- Listings will be sorted by treatment group (see Section 6.1.1 for ordering), patient number and, if applicable, by assessment date and time unless otherwise noted. Patients who are screen failures will be presented in a separate listing.
- The total number of patients in the treatment group and dose level (N) will be used as the denominator for percentage calculations, unless stated otherwise in the table shell.
- Continuous variables, including pharmacodynamic variables, will be summarized using the number of observations (n), mean, standard deviation (StD), median,

## Statistical Analysis Plan

minimum, and maximum, unless otherwise specified. The descriptive statistics to be provided for PK data are summarized in Section 6.1.2.

- For log transformed data it is more appropriate to present geometric mean, coefficient of variation (CV), arithmetic mean, SD, median, minimum and maximum.
- Categorical variables will be summarized using number of observations (n), frequency and percentages of patients.
- Multiple assessments at a given time point (planned, repeat, unscheduled) will not be included in summary tables unless otherwise specified, but will be included in the listings and patient profiles if required. For example, if there are multiple laboratory results at a given visit, the latest non-missing value will be included in summary tables.

### 6.1.1. Presentation of Data by Treatment Group

Data will be summarized separately for each of the 2 treatment combinations (AZD9150/MEDI4736, and AZD5069/MEDI4736) in Part A. Each treatment combination will be presented in separated pages of one table.

IO Naïve 1st Line Combo, consisting of 10 identified B3 patients and all B7 patients, and IO Naïve 2nd Line+ Combo Population, consisting of all B3 subjects not in the previous group will be included in all summaries and analyses and will be presented as any treatment group is presented.

Patients who have a dose modification during the trial will be presented according to the dose group to which they were initially assigned.

### 6.1.2. Descriptive Statistics for PK Data Summaries

The following summary statistics will be presented for plasma concentrations at each time point and PK parameters, AUC, AUC(0-6), AUC(0-8), AUC(0-10), AUC(0-12), AUC(0-48), AUC(0-t), AUC(0- ), Rac, Cmax, Css max, Ctrough, Css min, and CEOI.

- Number of observations
- The geometric mean (gmean) calculated as  $\exp[\mu]$ , where  $\mu$  is the sample mean of the data on a logarithmic scale

## Statistical Analysis Plan

- Coefficient of variation, calculated as  $100 * [\exp(s^2) - 1]^{1/2}$ , where s is the standard deviation of the data on a log-scale
- Gmean + standard deviation (calculated as  $\exp[\mu \pm s]$ )
- Gmean - standard deviation (calculated as  $\exp[\mu \pm s]$ )
- Arithmetic mean calculated using untransformed data
- Standard deviation calculated using untransformed data
- Median
- Minimum
- Maximum

The following summary statistics will be presented for CL, CL/F, CLss/F, CLR, MRT, Vss, Vss/F, Vz, Vz/F, t1/2λz, MR, Rac, TCP, Ae, and %Fe:

- Number of observations
- Arithmetic mean
- Standard deviation
- Median
- Minimum
- Maximum

For Tlast, Tmax and Tmax ss, only the number of observations, median, minimum, and maximum will be presented in summary tables. The PK data for AZD9150, MEDI4736, AZD5069, and treme will also be displayed graphically as appropriate. Displays will include individual patient plasma concentration versus time profiles (on the linear and log-scale) versus time and gmean concentration (± standard deviation) versus time profiles, stratified by cohort and other groupings, as necessary.

## Statistical Analysis Plan

### 6.2. KEY DEFINITIONS

For the purposes of this study, the term “study drug” is restricted to AZD9056, AZD9150, MEDI4736, treme, and the 4 drug combinations, AZD9056/MEDI4736, AZD9150/MEDI4736, AZD9056/MEDI4736/treme and AZD9150/MEDI4736/treme.

Study Day is the day relative to the date of the first dose of study drug in Cycle 1. If a date falls on or after the date of the first dose in Cycle 1, then the corresponding Study Day is calculated as (Study date) – (Date of first dose in Cycle 1) + 1. If a date falls before the date of first dose in Cycle 1, the corresponding Study Day is calculated as (Study date) – (Date of first dose in Cycle 1). Day -1 is the day immediately before the date of the first dose in Cycle 1.

The last dose date is defined as the last non-missing date where a non-zero dose of study drug was recorded. For patients who are ongoing at the time of an interim analysis, the last dose date will be considered the date of the most recent study visit in the database for that patient where a non-zero dose of study drug was recorded.

Unless otherwise specified, baseline is the last non-missing observation before the start of study treatment in Cycle 1.

In treatment arm A1 (AZD9150/MEDI4736), A4 (AZD9150/MEDI4736 or AZD9150/MEDI4736/treme) in dose escalation Part A, an evaluable patient must have received all 3 loading doses of AZD9150 during the 7-day Lead-in period and at least 3 additional doses during Cycle 1 as well as the MEDI4736 and treme infusion during the DLT Evaluation period or have suffered a DLT within the first 35 days of treatment. In treatment arm A2 (AZD5069/MEDI4736) in dose escalation Part A, an evaluable patient must have received all doses during the 7-day Lead-in period (i.e., 14 doses) and at least 42 additional doses as well as the MEDI4736 infusion during the DLT Evaluation period or have suffered a DLT during or before the first 35 days of treatment.

An efficacy evaluable patient is defined as a patient with unidimensional measurable disease at baseline as per the RECIST version 1.1 criteria who received at least 1 dose of study treatment.

A cycle length is 28 days. The follow-up visit will occur 28 days after the last dose of study treatment with a window of +7 days. Patients who discontinue treatment for reasons other than PD will undergo follow-up tumour assessments every 2 months until PD is noted. To facilitate the scheduling of tumour assessments, a window of  $\pm 3$  days is allowed.

